2.1 Recruitment and Randomization

The trial is approved by the local Ethics Committee (LocalNo.125222022) according to the Helsinki Declaration of 1964. Patients' legal guardians will provide written informed consent.

Fifteen Children between 3 and 5 years of age scheduled for elective surgery will be prospectively enrolled at the Department of Pediatric Surgery, University Hospital of Messina, Italy. Inclusion criteria are the need for elective surgery, in the morning time. Exclusion criteria are children with cerebral malformations and/or injuries, or surgery in the afternoon or at night to eliminate conditions that could affect melatonin production. Children will be also excluded in cases of withdrawal of informed consent, insufficient blood samples, and hemolysis of the blood sample, as hemolysis interferes with the biochemical determination of the OS biomarkers.

Infants matching the clinical criteria for inclusion in the study will then be randomized to be premedicated with oral melatonin (Mel group) or 5% dextrose (Control group)

Permuted, block randomization will be performed by a biostatistics using computerized sequences, and group assignments will be provided in concealed opaque envelopes. Parents of participants will be informed of their infant's group allocation at discharge.

Interventions

- *Mel group:* Melatonin (Dicoson, Dicofarm, Italy, 5 drops = 1 mg) will be administered orally.

The product is listed in the Register of Dietary Supplements on the website of the Ministry of Health (<http://www.ministerosalute.it/alimenti/dietetica>) and is classified with the following code: 943314283. This product is subject to the European Directive on Foodstuffs according to DL n. 169 of May 21, 2004, and not to the European Directive on Medicines 2001/20/EC transposed at the Italian level with D.L. n. 211 of June 24, 2003. Melatonin administration has a good safety profile, with no known adverse effects. Approximately 1 hour before induction of anesthesia, patients will receive oral melatonin or placebo. Mel treated children received a single dose of oral melatonin 0.5 mg/kg (for a max 10 mg). Melatonin (Dicoson, Dicofarm, Italy) will be prepared by a dedicated resident in a fixed volume of 5 mL by adding water to a syringe without a needle.

- *Control group:* Approximately 1 hour before induction of anesthesia, patients will receive 5 mL of 5% dextrose (placebo), used to simulate the sweet taste of the melatonin formulation.

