2.3 Perioperative management of children, analgesia and anesthesia

The induction of general anesthesia will be obtained in all children through bolus doses of 1 mg/kg over 20 s of intravenous propofol, followed by similar bolus doses of propofol until the patient will be anesthetized, and anesthesia was maintained with inhaled sevoflurane.

Children will be considered anesthetized when they are asleep and unarousable, and the eyelash reflex disappear. Thereafter, anesthesia will be maintained with inhaled sevoflurane.

At the end of the surgery, after returning to the ward, all patients will be assessed for postoperative pain using the Face, Legs, Activity, Cry, and Consolability (FLACC) scale. If FLACC score is greater than 3, the analgesic drug paracetamol will be administered at the dose of 15 mg/kg, every six hours at most. Clinical and research personnel will be unaware of the group assignments until the completion of data analysis. The number of doses of paracetamol administered to children of both treatment conditions within 48 hours after surgery, even if discharged, will be recorded.

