2.4 Melatonin, 4-Hydroxynonenal, and SIRT1 Measurements

Samples of 0.2 mL of plasma will be collected at T0 (pre-hospitalization, 1 day before surgery), T1 (after anesthesia, immediately before surgery) and T2 (at 1 h after the end of the surgery and awakening after anesthesia), and biochemical analyses will be performed.

Melatonin plasma levels will be assessed at each experimental time point (T0, T1, T2) using a competitive enzyme-linked immunosorbent assay (cELISA) kit from Antibodies.com (A87093) according to the manufacturer's instructions. T1 and T2 plasma samples from Mel treated children suspected of containing concentrations higher than the highest standard (500 pg/mL) will be diluted 1:100 (v/v) with sample diluent prior to analysis. Color development will be monitored at 450 nm in a Thermo Scientific (MultiSkan FC) microplate reader, and a standard curve (range 7.813-500 pg/mL) will be generated using a four-parameter logistic (4-PL) curve fit.

4-Hydroxynonenal (4-HNE) as a marker of lipid peroxidation will be measured to evaluate OS by using a cELISA kit from Antibodies.com (A86962). Plasma concentrations will be calculated by reading the absorbance at 450 nm and referring to the standard curve (range 31.25-2000 pg/mL). SIRT1 will be quantified using an ELISA kit from Invitrogen (EH427RB). Plasma samples will be diluted 1:2 as indicated by the Manufacturer before analysis. SIRT1 concentrations will be calculated by absorbance reading at 450 nm and referring to the standard curve (range 1.23-300 ng/mL).

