2.5 Quantitative real-time PCR for mature microRNAs analysis

MicroRNA analyses will be performed based on the quali-quantitative plasma sample available (N=3 at each time point, T0, T1, and T2). MicroRNAs (miR-34 and miR-124a) will be isolated from plasma using the Norgen total RNA isolation kit¹. The Plasma microRNAs and spike-in cel-miR-39 expressions will be evaluated using the TaqMan miRNA assay. The TaqMan miRNA reverse transcription kit will be used to reverse transcribe miRNAs. Subsequently, RT-qPCR will performe in 20 µL of PCR mix containing 1 µL of 20× TaqMan miRNA assay, which contained PCR primers and probes (5'-FAM), 10 µL of 2×TaqMan Universal PCR Master Mix No Amp Erase UNG and 5 µL of reverse-transcribed product. The reaction will be first incubated at 95 °C for 10 min followed by 40 cycles at 95 °C for 15 s and at 60 °C for 1 min. The quantitative real-time PCR (RT-qPCR) will be performed on a ABIPRISM 7500 Real Time PCR System. Data will be analyzed by a 7500-system software (1 1.4.0) with the automatic comparative threshold (Ct) setting for adapting baseline. Detection thresholds were set at 35 Ct. The relative amounts of miR-34 and miR-124a will be calculated using the Ct method: $\Delta Ct = Ct (miR-34/miR-124a) - Ct (reference miRNA); 2^{-\Delta Ct}$.

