2.6 Data analysis

Data will be expressed as mean (standard error, SE) or median (interquartile range, Q1-Q3) as appropriate. Differences between T0, T1, and T2 will be analyzed by repeated measures ANOVA followed by Tukey's multiple comparison test for melatonin, 4-HNE, miR34 and miR124a plasma levels, while by Friedman test followed by Dunn's test in the case of SIRT1 levels. At each experimental time point, comparisons between the Control and Mel treated children will be performed using Student's t-test for unpaired data or Mann-Whitney U test as appropriate. Linear regression analyses will also be performed to examine correlations between variables (Pearson correlation). All data with P < 0.05 will be considered statistically significant. GraphPad Prism 6.0 (GraphPad Software, Inc., San Diego, CA, USA) will be used for statistical analysis.

References

Fischer S, *et al.* Role of anxiety in young children's pain memory development after surgery. *Pain* 160, 965-972 (2019).

Perrone S, *et al.* Oxidative Stress as a Physiological Pain Response in Full-Term Newborns. *Oxid Med Cell Longev* 2017, 3759287 (2017).

Marseglia L, *et al.* Antioxidant Effect of Melatonin in Preterm Newborns. *Oxid Med Cell Longev* 2021, 6308255 (2021).

Perrone S, *et al.* Melatonin in Newborn Infants Undergoing Surgery: A Pilot Study on Its Effects on Postoperative Oxidative Stress. *Antioxidants (Basel)* 12, (2023).

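### A failed T1 or T2 blood sample, read literally, excludes the randomised child rather than the assay value, and with the child go pain data that need no blood

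*Combined protocol and SAP*

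**What the plan says.** Section 2.1 lists the exclusion criteria and then adds: "Children will be also excluded in cases of withdrawal of informed consent, insufficient blood samples, and hemolysis of the blood sample". The only reason given is "as hemolysis interferes with the biochemical determination of the OS biomarkers". Eligible children are then randomised, and the Interventions part of the same section gives the time of dosing: "Approximately 1 hour before induction of anesthesia, patients will receive oral melatonin or placebo".

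Section 2.4 takes blood at T0, the day before surgery, and then at "T1 (after anesthesia, immediately before surgery) and T2 (at 1 h after the end of the surgery and awakening after anesthesia".

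Section 2.3 says that after return to the ward "all patients will be assessed for postoperative pain" on the FLACC scale. It also has the following recorded, discharged children included: "The number of doses of paracetamol administered to children of both treatment conditions within 48 hours after surgery".

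Section 2.5 works at the level of the sample: "MicroRNA analyses will be performed based on the quali-quantitative plasma sample available", with three samples per time point.

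Section 2.6 compares the groups at each time point with an unpaired t-test or Mann-Whitney test. Change over time is tested by repeated-measures ANOVA, or by "Friedman test followed by Dunn's test in the case of SIRT1 levels". The section defines no analysis set and no rule for missing data or replacement, and it names no test specifically for FLACC or paracetamol.

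**The concern.** The reason given for the haemolysis exclusion justifies discarding an assay result. It gives no ground for discarding a pain score or a dose count. Postoperative pain is half of the hypothesis in Section 1, and neither of its measures needs blood.

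If the rule is applied as worded, a laboratory problem after treatment shrinks an already small pain comparison, and that comparison no longer covers all children as randomised. Valid assay results from the child's other samples would go too.

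There is also a risk of bias if sample failure is related to arm or to pain. In my judgement a route exists at T2, where a distressed, awake child may be harder to bleed. I see none at T1, when the child is under anaesthesia. The documents do not show that either happens.

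**Working it through.** **Order of events (Sections 2.1, 2.3 and 2.4)**

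1. T0 sample, the day before surgery.
2. Randomisation (exact time not given), then premedication about 1 h before induction.
3. Induction, then the T1 sample, then surgery.
4. FLACC on the ward, and the T2 sample at 1 h.
5. Paracetamol doses counted to 48 h.

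A T1 or T2 failure can be known only after the child has been randomised and dosed. A T0 failure found before randomisation would be an ordinary screening exclusion and is left out below.

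**Inputs**

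- From the plan: 15 children (Section 2.1), two post-randomisation samples per child (Section 2.4), significance at 0.05 (Section 2.6).
- Assumed, because the plan does not give them: failure probability q per sample of 2%, 5% or 10%; independent failures; an 8 v 7 split; two-sided testing; a true difference of 1.0 or 1.5 SD.

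The plan states no failure rate, power or effect size, so there is no figure of its own to reproduce.

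**Children lost through T1 or T2**

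Probability per child p = 1 − (1 − q)². Expected loss = 15p. Chance of losing at least one child = 1 − (1 − p)^15.

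| q | p | Expected loss of 15 | Chance of at least one |
|---|---|---|---|
| 2% | 1 − 0.98² = 3.96% | 0.59 | 45% |
| 5% | 1 − 0.95² = 9.75% | 1.46 | 79% |
| 10% | 1 − 0.90² = 19.0% | 2.85 | 96% |

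Independence gives the larger loss. If a child's T1 and T2 samples always failed together, p would equal q. The expected loss would then be 0.3, 0.75 or 1.5 children, and the chance of losing any child 26%, 54% or 79%.

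**Effect on a two-group comparison**

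Half-width of the 95% confidence interval, in SD units: t(0.975, n₁ + n₂ − 2) × √(1/n₁ + 1/n₂). For 8 v 7 this is 2.160 × 0.5175 = 1.118. Power comes from the noncentral t distribution with noncentrality d / √(1/n₁ + 1/n₂).

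| Children lost | Split | Half-width (SD) | Change | Power at 1.5 SD | Power at 1.0 SD |
|---|---|---|---|---|---|
| 0 | 8 v 7 | 1.118 | – | 76.4% | 43.2% |
| 1 | 7 v 7 | 1.165 | +4.2% | 73.1% | 40.6% |
| 2 | 7 v 6 | 1.225 | +9.5% | 69.0% | 37.5% |
| 3 | 6 v 6 | 1.286 | +15.1% | 65.0% | 34.7% |

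These figures are t-based and only approximate for an ordinal score such as FLACC or a count of doses. They illustrate the scale of the loss; they do not describe a pain test that the plan specifies.

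**With assay-level missingness**

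A failed sample would remove no child. All 15, consent permitting, would stay in the FLACC and paracetamol comparisons, and valid results at other time points would remain usable.

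**The case against.** The sentence names no time point and stands among the eligibility criteria, just before the statement that eligible children are then randomised. It could therefore be meant for T0. Section 2.3 has every patient assessed for pain, Section 2.5 uses whatever plasma is available, and the stated reason concerns the assays alone. All of this suggests that the authors may never have meant to drop pain data. Staff also stay blind until the analysis is complete, so exclusions would be made blind. Finally, the loss of one child costs little precision, which a pilot can bear.

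Part of this stands. The loss of pain data is an inference from the wording, bias is not shown, and blinding guards against deliberate selection. A child without a 4-HNE value also drops out of the planned pain and 4-HNE correlation under any rule. Likewise, for a given analyte, the planned within-child tests need all three time points.

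The rest does not settle the matter. Withdrawal of consent is in the same list and can occur at any time, so the sentence is not confined to screening. Section 2.3 says who is assessed, not who is analysed, and nothing in Section 2.6 overrides the exclusion. Blinding does not restore lost children, nor does it remove bias if failure itself depends on pain or arm.

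**Conclusion.** The concern holds. As worded, the rule takes the child as the unit of exclusion, and T1 and T2 failures necessarily come after randomisation and dosing. The affected assay value is lost under any rule. The avoidable loss is FLACC, paracetamol and the child's valid samples.

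On assumed failure rates of 2% to 10% per sample, the expected loss is about 0.6 to 2.9 of 15 children if failures are independent, and 0.3 to 1.5 if they coincide fully. A single lost child matters little for precision; three would widen the interval by about 15%. The conclusion rests on the wording and the timing of the samples. The figures depend on the assumed failure rates, split and effect size, and the direction of any bias is unknown. This should be corrected because the loss is avoidable at almost no cost.

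**What to change.** In Section 2.1, keep withdrawal of consent as a separate ground, and say what happens to data collected before withdrawal. Replace the sample clause with wording such as:

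> A sample that is haemolysed or too small is set to missing only for the affected assay at that time point, decided before unblinding. All randomised children with consent remain in the FLACC and paracetamol comparisons, and in every assay and time point with a valid sample, analysed as randomised. Failed samples are reported by arm and time point.

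In Section 2.6, state that between-group tests at each time point use all available values. For the within-child comparisons (repeated-measures ANOVA, and Friedman for SIRT1), choose in advance either a method that accepts missing time points or a complete-case analysis with the number of children stated. Name the tests for FLACC and paracetamol and the set of children to which they apply.

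The change is to protocol wording only and needs no extra children, samples or procedures. Denominators will differ slightly between outcomes and must be shown with each result.

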Several studies have shown that lipid peroxidation is involved in different types of pain, such as cancer pain, fibromyalgia, and neuropathic pain. 4-HNE plasma levels are good indices of free radical damage on lipids. Lipid damage from free radical exposure leads to lipid hydroperoxide generation from lipids and to carbonyl formation and protein hydroperoxide generation from proteins. Lipid peroxidation reaction leads to increased endogenous production of reactive aldehydes and their derivatives, such as malondialdehyde and 4-HNE²⁰. Malondialdehyde is the most mutagenic by-product of lipid peroxidation, while 4-HNE is the most toxic. 4-HNE is often used as a marker of OS and has been implicated in the pathogenesis of cancer, neurodegenerative diseases, diabetes, and other diseases. 4-HNE is involved in many pathophysiological signaling pathways SIRT1, acting as a NAD⁺-dependent deacetylase, plays a crucial role in critical cellular functions such as energy metabolism, genomic stability, inflammation, and immune response. Due to its multifunctional role, SIRT1 has been considered a promising target for therapies aimed at treating various conditions, including metabolic disorders and age-related diseases. Decreased SIRT1 levels have been observed in the spinal cord of various pathological pain models, in which SIRT1 activation helped alleviate chronic pain by regulating inflammation, oxidative stress, and mitochondrial dysfunction.

Recent animal studies have demonstrated that miRNAs are involved in pain processing pathways. Ikuma et al. found the increased extracellular release of microRNAs from dorsal root ganglion cells in a rat model of neuropathic pain.

In this prospective, randomized, double-blind pilot study, we test the hypothesis that melatonin, administered as premedication before induction of anesthesia, reduces OS and postoperative pain involving the sirtuin pathway in children undergoing minor abdominal surgery.

The relationship between pain and 4-HNE, between 4-HNE and melatonin levels, and between microRNAs and SIRT1 levels will be investigated.

2. Methods

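### Parents learn the treatment arm at discharge while the 48-hour paracetamol count is still running, so any doses given at home are counted unblinded

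*Combined protocol and SAP*

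**What the plan says.** Four statements bear on this point.

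- Disclosure (section 2.1): "Parents of participants will be informed of their infant's group allocation at discharge".
- The count (section 2.3): paracetamol doses in both arms "within 48 hours after surgery, even if discharged, will be recorded". The plan thus foresees discharge inside the window and means to keep counting afterwards.
- Who stays blinded (section 2.3): "Clinical and research personnel will be unaware of the group assignments until the completion of data analysis". Parents are not included.
- The label and the aim (end of section 1): "In this prospective, randomized, double-blind pilot study", testing whether melatonin "reduces OS and postoperative pain involving the sirtuin pathway in children undergoing minor abdominal surgery".

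On the ward, a dose depends on a FLACC score above 3, and the assessment is placed there: "after returning to the ward, all patients will be assessed for postoperative pain". For the time at home, the plan does not say who judges pain, who decides on a dose or how doses are recorded. No section delays the disclosure.

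**The concern.** Less postoperative pain is part of the hypothesis. The plan has two pain-related measures, the FLACC score and the paracetamol count, and only the count has a stated 48-hour window that runs past discharge. Parents who have been told that their child received melatonin, or only dextrose, may give paracetamol more or less readily, or report it differently. The likely direction is fewer doses in the melatonin arm or more in the control arm. Either would look like an analgesic effect.

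There is a second route. Informed parents could reveal the arm to staff whom section 2.3 keeps blinded, including whoever collects the 48-hour record. The plan does not say who tells parents the allocation while clinical and research staff stay unaware of it.

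**Working it through.** The plan gives no figure to reproduce here. The check is a comparison of the text, followed by arithmetic on stated assumptions.

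**1. Which data are exposed**

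| Measure | When taken | Parents already told? |
|---|---|---|
| Melatonin, 4-HNE, SIRT1, microRNAs | Up to "T2 (at 1 h after the end of the surgery and awakening after anesthesia" (section 2.4) | No |
| FLACC on the ward | Before discharge | No |
| Paracetamol before discharge | Before discharge | No |
| Paracetamol after discharge, up to 48 h | After discharge | Yes |

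**2. How much of the window is exposed**

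The exposed time is 48 − d hours for discharge at d hours. The values of d are assumed, because the plan gives none.

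| d (h) | Exposed (h) | Share of 48 h | Six-hour intervals exposed, of 8 |
|---|---|---|---|
| 6 | 42 | 88% | 7 |
| 12 | 36 | 75% | 6 |
| 24 | 24 | 50% | 4 |
| 36 | 12 | 25% | 2 |
| 48 or later | 0 | 0% | 0 |

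**3. Fewer home doses in the melatonin arm (illustration)**

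From the plan: 15 children in total (section 2.1) and a 5% significance level (section 2.6). Assumed: 7 melatonin v 8 control, Poisson counts, no drug effect, a two-sided pooled t-test, and home doses lower by a fraction r in each affected melatonin child. Each cell uses 200,000 simulated trials.

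False difference in means = mean home doses × r × share of melatonin children affected.

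False-positive rate (%), 4 expected doses per child:

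| Ward + home doses | Melatonin children affected | r = 10% | 20% | 30% | 50% |
|---|---|---|---|---|---|
| 1 + 3 | all | 5.6 | 8.4 | 13.3 | 31.0 |
| 2 + 2 | all | 5.3 | 6.4 | 8.4 | 15.4 |
| 3 + 1 | all | 5.0 | 5.3 | 5.7 | 7.2 |
| 1 + 3 | half | 5.2 | 5.7 | 6.8 | 10.6 |
| 2 + 2 | half | 5.0 | 5.3 | 5.7 | 7.4 |
| 3 + 1 | half | 4.9 | 5.1 | 5.1 | 5.4 |

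- With r = 0, which is what blinded parents correspond to, the rate is 4.9% in all three splits.
- Ward doses analysed alone (means 1, 2, 3) give 4.6%, 4.9% and 5.0%, so they show no inflation.
- With 2 expected doses, the highest rate is 17.2% (0.5 + 1.5, r = 50%, all affected).
- With 8 melatonin v 7 control, the worst cell is 32.5% instead of 31.0%.
- Smallest false difference, over both dose levels: 0.5 × 0.10 × 0.5 = 0.025 doses, and 0.025 / 2 = 1.25% of the control mean.
- Largest: 3 × 0.50 × 1 = 1.5 doses, and 1.5 / 4 = 37.5%.

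**4. Extra doses in the control arm (illustration)**

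Control parents are told their arm too. Assumed: 8 control v 7 melatonin, a true mean of 1 to 3 doses, counts capped at 8, and 4,000 simulated trials per scenario. Ranges cover the t-test and the Mann-Whitney test.

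| Extra control doses | False-positive rate |
|---|---|
| 0 | about 4–6% |
| 0.5 | about 6–12% |
| 1 | about 14–29% |
| 2 | about 38–72% |

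The 31% to 33% in step 3 is therefore the edge of one set of assumptions and not an upper bound.

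**The case against.** The strongest reply is that the harm is conditional and the outcome may carry little weight.

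- *Discharge might come after 48 hours.* If every child stayed that long, nothing would be exposed. The plan gives no discharge time, so this is possible. But section 2.3 expressly provides for counting after discharge, so earlier discharge is expected for at least some children.
- *The parents' role is inferred.* No section says that they decide on, give or report home doses. This stands. However, the plan describes no other source for those doses, and the children are 3 to 5 years old.
- *The count is not called primary and has no named test.* This stands. Section 2.6 says: "At each experimental time point, comparisons between the Control and Mel treated children will be performed", which does not cover a 48-hour count. The false-positive rates above therefore belong to a test that the plan does not specify. But no outcome is labelled primary, and the count is required in both arms. If reported, it would bear on the claim about pain.
- *The simulated rates rest on assumptions.* This stands too. With the Mann-Whitney test, which section 2.6 also allows, the worst 7 v 8 cell falls slightly (28.7% against 31.1% for the t-test in the same run). The rates show what could happen and predict nothing.

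These points limit the weight of the concern. None of them removes the overlap.

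**Conclusion.** The concern holds. As written, the plan unblinds parents while a pain-related measure is still accruing for any child discharged before 48 hours, and this does not fit the double-blind label. That much follows from the text alone. That the count would be biased, in which direction and by how much are inferences that depend on parents controlling or reporting home doses. Within the assumptions shown, the effect runs from nothing visible to a substantial excess of false positives. It is confined to doses after discharge. This should be fixed: the effect is conditional and touches one outcome, but bias in unblinded home doses cannot be removed afterwards and the remedy is cheap.

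**What to change.** Replace the disclosure sentence in section 2.1 with: *Parents will be informed of the group allocation only after the 48-hour paracetamol record for their child has been collected.* Make the same change in the parent information.

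This protects the count but still leaves parents informed before the analysis is complete, so they could reveal the arm to staff. Holding disclosure until the analysis is finished closes that route as well and matches the staff blinding in section 2.3.

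If disclosure at discharge has to stay, record for each dose whether it was given before or after discharge, and report the later doses separately as unblinded.

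Cost: one sentence, and parents learn the allocation later. Disclosure can follow the contact that collects the home doses, if there is one. The plan does not describe how they are collected, so a contact may have to be added. Waiting until the analysis is complete may need one further contact per family, up to 15. The fallback needs one extra field per dose and leaves the home doses unblinded. None of these changes alters a dose, a sample or a clinical rule.

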The contents of the syringe will be blindly administered to the patients by the attending nurse, who will not be involved in the study.

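### Telling parents the allocation at each child's discharge opens a route by which later permuted-block assignments could be partly predicted, and sits uneasily with the staff-blinding statement

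*Combined protocol and SAP*

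**What the plan says.** The combined protocol and SAP, section 2.1, describes a single-department trial: "Fifteen Children between 3 and 5 years of age scheduled for elective surgery will be prospectively enrolled". On allocation it says: "Permuted, block randomization will be performed by a biostatistics using computerized sequences, and group assignments will be provided in concealed opaque envelopes". It then adds: "Parents of participants will be informed of their infant's group allocation at discharge".

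Section 2.3 makes a broader promise about staff: "Clinical and research personnel will be unaware of the group assignments until the completion of data analysis".

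The Interventions text in section 2.1 says that the melatonin "will be prepared by a dedicated resident in a fixed volume of 5 mL", and that the syringe contents are to be "blindly administered to the patients by the attending nurse, who will not be involved in the study".

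The plan does not state the block size, whether it is fixed or varying, the allocation ratio, how the envelopes are numbered and held, who tells the parents, or how fast children will be enrolled.

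**The concern.** A permuted block forces balance. An opaque envelope therefore hides the next assignment fully only while the earlier assignments in the same block stay hidden. Disclosure at discharge releases those assignments one at a time, possibly while later children are still being allocated from the same list. Someone must look up each allocation and pass it on, and parents who have just been told may mention it on the ward.

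Two things are at stake if the information reaches the wrong people. Whoever approaches or schedules children could, knowingly or not, let a foreseen arm influence who comes next. And whoever scores FLACC, an observer-rated scale that also triggers paracetamol, could score a child whose arm they think they know. With 15 children, one steered child is 1/15 = 6.7% of the sample. That is a measure of how small the trial is, not an estimate of bias.

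This is separate from the discharged child's own 48-hour paracetamol count, which may still be running when the parents are told. Delaying each disclosure to 48 hours would protect that count but would still release the sequence during recruitment.

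**Working it through.** **Inputs.** From section 2.1: 15 children, permuted blocks, disclosure at each discharge. Assumed, because the plan is silent: 1:1 allocation; one fixed block size of 2, 4, 6 or 8, known to the person guessing; and 0 to 3 of the most recent children not yet discharged when the next is allocated. The guesser picks the arm with more places left in the block and tosses a coin when they are equal. The plan gives no predictability figure, so there is nothing of its own to reproduce. Fifteen is odd, so under 1:1 even blocks the last block is incomplete.

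**Ceiling: every earlier allocation known.** For a complete block of size 2m:

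- expected share certain = 1/(m+1)
- expected share guessed correctly = 1/2 + (4^m / C(2m,m) − 1)/(4m)

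Certain assignments among 15:

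- Blocks of 2: 7 complete blocks × 1 = 7.0; the 15th child opens a new block and adds none.
- Blocks of 4: 3 × 4/3 = 4.0. In the unfinished block the third child is certain if the first two match, probability 1/3. Total 4.33.
- Blocks of 6: 2 × 6/4 = 3.0; none of the first three of the next block can be certain.
- Blocks of 8: 8/5 = 1.6, plus a second block without its always-certain last place, 1.6 − 1 = 0.6. Total 2.2.

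Correct guesses among 15:

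- Blocks of 2: 7 certain + 8 × 0.5 = 11.0 (73.3%).
- Blocks of 4: 4 × 0.7083 = 2.833 per block; 3 × 2.833 + (2.833 − 1) = 10.33 (68.9%).
- Blocks of 6: 6 × 0.6833 = 4.1 per block; 2 × 4.1 + (0.5 + 0.6 + 0.6) = 9.9 (66.0%).
- Blocks of 8: 8 × 0.6661 = 5.329 per block; 5.329 + (5.329 − 1) = 9.66 (64.4%).

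**Overlapping stays.** A simulation of 40,000 sequences per setting matches the first row to within 0.1 percentage point and supplies the rest. Where no earlier member of the block is known, the value is exactly 50%. Cells show the percentage of correct guesses, then the number certain out of 15.

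| Children not yet discharged | Blocks of 2 | Blocks of 4 | Blocks of 6 | Blocks of 8 |
|---|---|---|---|---|
| 0 | 73.3%; 7.0 | 68.9%; 4.3 | 66.0%; 3.0 | 64.4%; 2.2 |
| 1 | 50.0%; 0 | 57.7%; 1.0 | 58.7%; 1.0 | 59.6%; 0.8 |
| 2 | 50.0%; 0 | 53.3%; 0 | 55.3%; 0.2 | 56.7%; 0.2 |
| 3 | 50.0%; 0 | 50.0%; 0 | 52.7%; 0 | 54.5%; 0.03 |
| No leak | 50%; 0 | 50%; 0 | 50%; 0 | 50%; 0 |

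Hand check for one undischarged child, blocks of 4: the four places have chances 1/2, 1/2, 2/3 and 2/3, a sum of 2.333. Then 3 × 2.333 + (2.333 − 0.667) = 8.67, or 57.8%, against 57.7% simulated.

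**Which row applies?** The accrual schedule is not given. If allocation to discharge takes about 2 days (an assumption), an average of one child awaiting discharge means 0.5 children a day, so 15/0.5 = 30 days of enrolment. An average of three means 1.5 a day, so 15/1.5 = 10 days. Slower enrolment moves the trial towards the top row. Several children allocated for the same morning would move it down.

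**The case against.** A reader might infer that staff can predict the next assignment and that concealment fails. The documents do not support that. Section 2.1 informs parents only, and section 2.3 says that personnel stay unaware. For harm to occur, the disclosed groups must reach someone on the ward, that person must collate them and know or infer an unstated block size and ratio, the relevant earlier child must already have been discharged, and the person must influence enrolment, scheduling or FLACC scoring. None of these steps is established.

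Nor do the two sections strictly contradict each other: they are compatible if someone outside the clinical and research team tells the parents. The consent form, which might say who does this, was not available for this assessment. The laboratory outcomes are also not open to scoring expectation; only selection could affect them.

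All of this stands, and it makes the top row of the table a ceiling rather than an expected value. It does not remove the point. The plan names no independent discloser, asks nobody to keep the information from staff, and does not defer disclosure until enrolment ends. The blinding statement in section 2.3 is an intention, and the procedure in section 2.1 opens a route around it.

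**Conclusion.** The point holds as an avoidable risk to allocation concealment and blinding, not as a demonstrated failure of either. For fixed 1:1 blocks of 2 to 8 known to the guesser, the exposure is at most 7.0 to 2.2 assignments certain and 73% to 64% of guesses correct. It drops to 50-60% correct and 0 to 1.0 certain with one child undischarged, and to 50-55% with almost none certain when three are. If nothing leaks, it is 50% and zero. The plan does not give the block size or accrual rate needed to say where in that range the trial would fall. The change is worth making because the sample is small, FLACC is observer-rated and the remedy is cheap.

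**What to change.** Amend section 2.1 so that parents are told the allocation only after the last child has been allocated and has completed the 48-hour follow-up. Waiting until data analysis is complete would also match section 2.3 as written. Either timing closes this route: guessing returns to 50% (7.5 of 15) with none certain, for any block size. If disclosure at discharge must stay, naming an independent discloser outside the clinical and research team is a weaker alternative, since parents could still tell the ward.

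Have the biostatistician use randomly varying block sizes withheld from the department, and state the allocation ratio and who holds the envelopes.

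Deferral does not remove what the resident who prepares the syringes already knows. State that this person takes no part in enrolment, scheduling or FLACC scoring, and qualify the section 2.3 statement accordingly.

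The cost is a change to the protocol and, where it covers disclosure, to the consent wording; parents learn the allocation later. Sample size and treatment are unaffected.
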